## INTRODUCTION AND PURPOSE

#### 1.1. Purpose

Current methods of wound closure including sutures, staples, skin adhesives, and alternative technologies are invasive, actively induce new scar through force concentration leading to focal tissue necrosis and can induce foreign body reactions. All of these factors can lead to scar induction above and beyond the scar directly attributable to the wound itself. Furthermore, current technologies fail to adequately control wound closure forces leading to tension on tissue in the wound zone. Unmitigated tension induces a cascade of tissue reactions including activation of mechanical tension receptors in the fibroblast/fibrocyte cell membrane which ultimately lead to increase fibroblast activation, chemotaxis, and increased collagen deposition, among other outcomes. The cumulative effect of these factors is increased scar burden, increased scar visibility, and an increased risk of pathological scars (hypertrophic scars and keloids).

## 2. BACKGROUND

Breast reduction surgery is an extremely common surgical procedure with over 97,000 cases performed in the United States in 2020, with approximately two-thirds done for reconstructive purposes, including alleviation of chronic shoulder, back and neck pain, and approximately one-third done for aesthetic purposes. Although satisfaction rates are high after reduction mammaplasty, complications can include wound infection, dehiscence, suture spitting, and hypertrophic scars, and revision of scars is common.

Force modulating tissues bridges (FMTB) represent a new class of wound closure and mechanomodulation devices which are non-invasive and designed to approximate wounds as well as off-load skin tension during both the immediate and ongoing wound healing phases in order to improve scar outcomes. Prior pre-clinical studies show that the devices are more effective than suture at off-loading skin tension and that they can provide superior skin eversion during closure. Initial clinical use began in September of 2020 and approximately 1000 clinical cases have been performed primarily in the plastic surgery and dermatological surgical areas. Initial clinical feedback based on survey results including 240 of the initial surgical procedures, including 108 bilateral mastopexy and breast reduction procedures incorporating vertical breast incision closure (216 breasts) suggests that the devices indeed improve initial scar outcomes, are well tolerated by patients with minimal skin reaction or irritation, and are anecdotally associated with a reduction in T-junction wound complications. This study is designed to confirm and quantitate these wound healing and patient benefits.

## 2.1. Rationale for Study Design

Given the large number of variables in wound healing leading to scar formation, including anatomical location, orientation, genetics, nutrition, disease states, ethnicity, etc., it is very difficult to effectively demonstrate improvement in scar appearance using parallel groups. Standard, symmetrical wound, self-controlled study designs have the advantage of accounting for all of these variables while decreasing the number of enrollees required for adequate sample size.

## 2.2. Sample Size/Power Analysis Factors:

The sample size calculation will be determined by the primary outcome: POSAS-O score. The study will enroll 42 patients which will allow us to detect a moderate effect (Cohen's d=0.5) in scar quality measured by POSAS-O with at least 80% power, accounting for an estimated 20% loss of patients.

In a study evaluating the effect of platelet-rich plasma glue on surgical scars following breast reduction mammoplasty, the control group had a mean POSAS-O score of 20.4 (SD 12.5) at 1-year. Although a minimal

clinically important difference (MCID) for POSAS has not been established in the literature, Cohen's d effect size (0.2 represents "small" effect, 0.5 represents "moderate" effect, 0.8 represents "large" effect) can be used to estimate a difference that may be clinically important.

	Effect Size (Cohen's d)			
	0.2	0.3	0.4	0.5
Change in POSAS-O score	2.5	3.75	5	6.25
Proportional change to	4.2%	6.3%	8.3%	10.4%
maximum POSAS-O score				

	Effect Size (Cohen's d)			
Power	0.2	0.3	0.4	0.5
80%	199	90	52	34
85%	227	102	59	38
90%	265	119	68	44

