## 3. CONCISE SUMMARY OF PROJECT

## 3.1. Clinical Study

This is a prospective, within-subject randomized, single blinded study designed to follow up to forty-two (42) qualified and consenting adult females, 18-70 years of age scheduled for elective breast reduction surgery using a standard inverted Wise (inverted "T") incision pattern. The sample size determination of this study is based on a structured power analysis using the observer portion of the Patient and Observer Scar Assessment Scale result as the primary outcome metric. Subjects will be randomized to the method of closure and wound support of the WISE-pattern incisions.

On the intervention side, subjects will have FMTBs applied for final layer closure of the vertical breast incision and, if eligible (incision >5cm in length), final layer closure of the lateral incision. Patients will continue with repeat application every two weeks for ongoing wound support for a total of 8 weeks of therapy. On the control side standard suture closure and wound dressings will be utilized. Patients will be evaluated at two-week intervals up until 8 weeks post-operative, then will have 3 additional follow up visits at 3-months, 6-months and 12-months post-operatively. The effects of the therapy will be analyzed during the follow up visits through photography, skin assessments and POSAS (Patient and Observer Scar Assessment Scale) results.

This is a single-site study at UT Southwestern Medical Center at Dallas in the Department of Plastic Surgery. The Principal Investigator has been selected based on his expertise, qualifications (credentials, training, and medical specialty), subject access, previous clinical research, facilities, and interest in this particular field of research. Subjects will be identified from the clinical practices of Drs. [name], [name], [name] at the University of Texas Southwestern Medical Center. All surgeries for this trial will occur at the Outpatient Building located on the UT Southwestern campus

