## Exclusion Criteria

- 1. Age less than 18 or greater than 70
- 2. Individuals diagnosed with known allergy to general adhesives/adhesive tape
- 3. Individuals with a history of using the following prescription medications:
  - Accutane within the past year;
  - Systemic steroid use within the past year
- 4. Individuals who have significant scarring on the test site/area(s)
- 5. Individuals with malnutrition
- 6. Individuals who have a body mass index >40
- 7. Individual who have a history of radiation therapy
- 8. Individual who have a history of breast cancer
- 9. Active smokers
- 10. Individuals with a disorder known to negatively affect wound healing (e.g. autoimmune disease, connective tissue disease
- 11. Individual who have an observable pre-operative or intra-operative breast asymmetry that, in the investigators opinion, would interfere with the evaluation of the efficacy of the wound therapy

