## 5.4. Randomization

Randomization via www.randomizer.org computer-based method: sealed pre-numbered randomization envelopes will be provided and opened by research staff and used to obtain randomization assignment. Unmasking of randomization assignment will occur after all portions of the surgical procedure are complete excepting only final skin layer closure and with intraoperative procedural symmetry confirmed.

Group 1				
Side 1	Side 2			
Final layer dermal closure with poliglecaprone 25	Final layer closure with force modulating tissue			
suture (Monocryl ® , Ethicon, Inc. Bridgewater, NJ)	bridges (FMTB) (Brijjit BP100-6, Brijjit Medical Inc.,			
	Marietta, GA)			
Group 2				
Side 1	Side 2			
Final layer closure with force modulating tissue	Final layer dermal closure with poliglecaprone 25			
bridges (FMTB) (Brijjit BP100-6, Brijjit Medical Inc.,	suture (Monocryl ® , Ethicon, Inc. Bridgewater, NJ)			
Marietta, GA)				

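### Does section 2.2 use two different meanings of Cohen's d, so that the power stated for d = 0.5 cannot be read in POSAS-O points?

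*Combined protocol and SAP*

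**What the plan says.** The protocol justifies its within-patient design in section 2.1 by noting that "self-controlled study designs have the advantage of accounting for all of these variables while decreasing the number of enrollees required". Section 2.2 sizes the trial on POSAS-O: 42 patients, to detect d = 0.5 "in scar quality measured by POSAS-O with at least 80% power, accounting for an estimated 20% loss of patients".

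Section 2.2 says that no minimal clinically important difference is established for POSAS. It offers Cohen's d instead, as something that "can be used to estimate a difference that may be clinically important", with 0.5 labelled moderate. For spread it cites a study in which "the control group had a mean POSAS-O score of 20.4 (SD 12.5) at 1-year".

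Two tables follow, both headed by Cohen's d at 0.2, 0.3, 0.4 and 0.5. The first has a row labelled "Change in POSAS-O score" (2.5, 3.75, 5 and 6.25) and expresses those points as percentages of the maximum score. The second gives sample sizes for 80%, 85% and 90% power. Nowhere do the documents give a between-breast correlation or an SD of within-patient differences, and section 2.2 names no test, alpha or sidedness.

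**The concern.** In a paired comparison, d is the mean within-patient difference divided by the SD of those differences. The 12.5 in the points row is the SD of single scores in one external group, which is a different quantity. A reader who goes down the d = 0.5 column will join 6.25 points to 34 patients at 80% power, and that step is valid only if the SD of differences happens to be 12.5.

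What would be at stake is the clinical reading of the target. If the two breasts of a patient were only weakly correlated, the trial would have clearly less than 80% power for 6.25 points. The gain from pairing that section 2.1 relies on depends on the same correlation, for which no value is given.

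**Working it through.** **Inputs.** From section 2.2: SD 12.5; d = 0.2 to 0.5; 42 enrolled; 20% loss; the 12 sample sizes. From Appendix I: six items scored 1 to 10, so the maximum is 60. Assumed because not stated: paired t-test, two-sided alpha 0.05, equal SDs on the two sides, and every value of the correlation r.

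**1. Points row.** d × 12.5 gives 2.5, 3.75, 5 and 6.25. Divided by 60, these are 4.2%, 6.3%, 8.3% and 10.4%. Both rows of the first table are reproduced.

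**2. Sample sizes.** Power comes from the noncentral t distribution with n − 1 degrees of freedom and noncentrality d√n. The smallest n that reaches each target is:

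| Power | d = 0.2 | 0.3 | 0.4 | 0.5 |
|---|---|---|---|---|
| 80% | 199 | 90 | 52 | 34 |
| 85% | 227 | 102 | 59 | 38 |
| 90% | 265 | 119 | 68 | 44 |

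All 12 cells match the plan. At 80% power the alternatives do not: one-sided paired t gives 156/71/41/27, the paired normal approximation 197/88/50/32, and a two-sample t-test 394/176/100/64 per group. The paired two-sided test is therefore a safe inference, and it fits the within-subject design in section 3.1.

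**3. What links the tables.** With equal SDs, the SD of differences is 12.5 × √(2(1 − r)). Setting this to 12.5 gives 2(1 − r) = 1, so r = 0.5. With unequal SDs the required r moves. If the device side had an assumed SD of 10.0, then 12.5² + 10² − 2r × 12.5 × 10 = 12.5², so 250r = 100 and r = 0.40.

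**4. The power claim that the plan makes (d = 0.5, 20% loss).** 42 × 0.8 = 33.6 completers.

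| Completers | Lost from 42 | Power at d = 0.5 |
|---|---|---|
| 34 | 8 (19.0%) | 80.8% |
| 33 | 9 (21.4%) | 79.5% |
| 42 | 0 | 88.6% |

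Linear interpolation at 33.6 gives 79.5 + 0.6 × (80.8 − 79.5) ≈ 80.3%. The claim fails, by half a percentage point, only if 33.6 is rounded down, and that is a loss above the planned 20%. Working forwards, 34/0.8 = 42.5, so 42 is right to rounding.

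**5. How far the points reading could move.** The r values are illustrative.

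| r | SD of differences | Points equal to paired d = 0.5 | Power for 6.25 points, n = 34 |
|---|---|---|---|
| 0 | 17.68 | 8.84 | 51.7% |
| 0.3 | 14.79 | 7.40 | 66.7% |
| 0.5 | 12.50 | 6.25 | 80.8% |
| 0.7 | 9.68 | 4.84 | 95.5% |
| 0.8 | 7.91 | 3.95 | 99.4% |

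The last column tests a claim that the protocol does not make. It shows sensitivity, not a shortfall.

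**The case for a change.** The strongest case for a change is that the points row exists so that d can be read on the scale. It sits under the same heading as the sample sizes, so readers will join the two, and one sentence would give the missing assumption. A single-score SD from one group cannot supply an SD of differences. Between r = 0.3 and r = 0.7, power for 6.25 points with 34 completers runs from 67% to 95%, which is not a trivial spread.

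Part of this stands. The assumption is unstated, the test and alpha have to be inferred, and the points row cannot be verified from the documents.

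The rest does not lead to a change:

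- The plan expresses its target as a moderate standardised effect and offers d itself as the yardstick. The points and percentage rows only illustrate it.
- The documents do not say which SD the authors meant. If 12.5 was their working value for the SD of differences, d has one meaning in both tables and nothing conflicts.
- Features of the design favour a positive correlation but fix no value. Section 5.3 excludes "breast asymmetry that, in the investigators opinion, would interfere with the evaluation of the efficacy of the wound therapy", and under section 5.4 the assignment is unmasked with all surgery done "excepting only final skin layer closure and with intraoperative procedural symmetry confirmed". Neither shows whether r is above or below 0.5.
- Without a source for r, a range over several assumed correlations would replace one unsourced value with several.

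**Conclusion.** No change is needed. Section 2.2 leaves a planning assumption unwritten, namely an SD of within-patient differences of 12.5, but no figure in it is shown to be wrong. Both tables reproduce exactly, and the stated power for d = 0.5 with 42 patients and 20% loss is correct to rounding (about 80.3% at 33.6 completers).

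The uncertainty is confined to translating d = 0.5 into points: 7.4 at r = 0.3, 6.25 at r = 0.5, 4.8 at r = 0.7. Its direction is unknown, so it gives no ground for raising or lowering enrolment. A paired analysis takes its standard error from the differences observed in the trial, so the planning SD does not enter the result. An analyst reading the sample-size table would recover the paired t-test without difficulty.

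This conclusion rests on the inferred test (two-sided 0.05 paired t, supported by 12 matching cells) and, for the points figures, on equal SDs and illustrative correlations. The gap is one of missing detail: filling it would make section 2.2 clearer and leave the trial as it is.

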## 3. CONCISE SUMMARY OF PROJECT

## 3.1. Clinical Study

This is a prospective, within-subject randomized, single blinded study designed to follow up to forty-two (42) qualified and consenting adult females, 18-70 years of age scheduled for elective breast reduction surgery using a standard inverted Wise (inverted "T") incision pattern. The sample size determination of this study is based on a structured power analysis using the observer portion of the Patient and Observer Scar Assessment Scale result as the primary outcome metric. Subjects will be randomized to the method of closure and wound support of the WISE-pattern incisions.

On the intervention side, subjects will have FMTBs applied for final layer closure of the vertical breast incision and, if eligible (incision >5cm in length), final layer closure of the lateral incision. Patients will continue with repeat application every two weeks for ongoing wound support for a total of 8 weeks of therapy. On the control side standard suture closure and wound dressings will be utilized. Patients will be evaluated at two-week intervals up until 8 weeks post-operative, then will have 3 additional follow up visits at 3-months, 6-months and 12-months post-operatively. The effects of the therapy will be analyzed during the follow up visits through photography, skin assessments and POSAS (Patient and Observer Scar Assessment Scale) results.

This is a single-site study at UT Southwestern Medical Center at Dallas in the Department of Plastic Surgery. The Principal Investigator has been selected based on his expertise, qualifications (credentials, training, and medical specialty), subject access, previous clinical research, facilities, and interest in this particular field of research. Subjects will be identified from the clinical practices of Drs. [name], [name], [name] at the University of Texas Southwestern Medical Center. All surgeries for this trial will occur at the Outpatient Building located on the UT Southwestern campus

## 3.2. Primary Outcomes

- Patient and Observer Scar Assessment Scale (POSAS)
- Photographic Assessment

## 3.3. Secondary Outcomes

- Scar volume/Surface area
- Gene regulation
- Genetic analysis
- Collagen volume/appearance on pathology
- Colorimetry
- Time of length of adherence
- Skin lab assessments (see below)

## 4. TEST MATERIAL INFORMATION

4.1 Study Material Description(s)

The following device will be evaluated during the study:

Proprietary Name	Device Description	Regulatory information
BRIJJIT BP100-6	Force Modulating Tissue Bridges for Cutaneous Wound Closure and Wound Support	Device Class 1 FDA Product Code KGX Regulation Number 21 CFR 880.5240

## 4.2 Study Device

BRIJJIT BP100-6 is a non-invasive wound closure device that reduces tension on scars and aids improving scar appearance.

Image 1- Fingertip Applicator	Image 2- Shield and adhesive		
Easy place and release applicator used to position the	Flexible bridge shields the wound during movement		
BRIJJIT device to the skin.	to promote healing and support.		

## 5. SUBJECT ENROLLMENT AND INSTRUCTIONS

## 5.1. Informed Consent Form

An IRB-approved informed consent form (ICF), consistent with the requirements in 21 Code of Federal Regulations (CFR) 50.25, will be given to each candidate subject before participation in any study procedures. The candidate subject will be given as much time as needed to read the ICF and will have the opportunity to have any study related questions answered to their satisfaction prior to signing the ICF. If further questions exist, the candidate subject will be given sufficient time during the first visit to clarify open questions and concerns regarding the study and/or the ICF with the Investigator, Sub-Investigator or the study coordinator prior to signing. An original signed copy for each subject participating in the study will be retained in the study file and each subject will receive a signed copy. The candidate subject will be ineligible to participate in this study without a signed ICF.

## 5.2. Subject Identification

Subjects will be assigned a 2-digit number which, when used in conjunction with the clinical study ID, will uniquely identify every subject on the study. This ID will remain with the subject throughout the study and should be used in all references to the individual in this study.

## 5.3. Eligibility Criteria

Inclusion Criteria

- 1. Healthy adult females 18-70 years of age
- 2. Planned procedure is bilateral breast reduction with modified Wise (anchor, inverted "T") scar pattern

- 3. Lateral incision measuring > 5 cm (for additional Brijjit application on lateral incision)
- 4. Ability to adhere wound therapy after surgery for 8 weeks or have a willing family member/partner to assist with wound therapy care.
- 5. Willing to follow wound care therapy as instructed by study staff.
- 6. Willing to return for follow up visits and undergo study evaluations.

## Exclusion Criteria

- 1. Age less than 18 or greater than 70
- 2. Individuals diagnosed with known allergy to general adhesives/adhesive tape
- 3. Individuals with a history of using the following prescription medications:
  - Accutane within the past year;
  - Systemic steroid use within the past year
- 4. Individuals who have significant scarring on the test site/area(s)
- 5. Individuals with malnutrition
- 6. Individuals who have a body mass index >40
- 7. Individual who have a history of radiation therapy
- 8. Individual who have a history of breast cancer
- 9. Active smokers
- 10. Individuals with a disorder known to negatively affect wound healing (e.g. autoimmune disease, connective tissue disease
- 11. Individual who have an observable pre-operative or intra-operative breast asymmetry that, in the investigators opinion, would interfere with the evaluation of the efficacy of the wound therapy

## 5.4. Randomization

Randomization via www.randomizer.org computer-based method: sealed pre-numbered randomization envelopes will be provided and opened by research staff and used to obtain randomization assignment. Unmasking of randomization assignment will occur after all portions of the surgical procedure are complete excepting only final skin layer closure and with intraoperative procedural symmetry confirmed.

Group 1				
Side 1	Side 2			
Final layer dermal closure with poliglecaprone 25	Final layer closure with force modulating tissue			
suture (Monocryl ® , Ethicon, Inc. Bridgewater, NJ)	bridges (FMTB) (Brijjit BP100-6, Brijjit Medical Inc.,			
	Marietta, GA)			
Group 2				
Side 1	Side 2			
Final layer closure with force modulating tissue	Final layer dermal closure with poliglecaprone 25			
bridges (FMTB) (Brijjit BP100-6, Brijjit Medical Inc.,	suture (Monocryl ® , Ethicon, Inc. Bridgewater, NJ)			
Marietta, GA)				

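### Patients are randomised to two mirror-image groups, but no blocking and no POSAS-O analysis with a side term are stated; pooling the groups would lose some precision if the two sides differ (minor)

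*Combined protocol and SAP*

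**What the plan says.** Section 3.1 describes the design: "This is a prospective, within-subject randomized, single blinded study designed to follow up to forty-two (42) qualified and consenting adult females". In section 5.4, Group 1 has suture on Side 1 and FMTB on Side 2, and Group 2 has the reverse. The mechanism is "Randomization via www.randomizer.org computer-based method: sealed pre-numbered randomization envelopes will be provided and opened by research staff". No ratio, block size or balance rule follows, and Side 1 and Side 2 are not tied to left and right.

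Section 2.1 justifies the design on the ground that "Standard, symmetrical wound, self-controlled study designs have the advantage of accounting for all of these variables".

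Section 2.2 says "The sample size calculation will be determined by the primary outcome: POSAS-O score" and that 42 patients will let the trial "detect a moderate effect (Cohen's d=0.5) in scar quality measured by POSAS-O with at least 80% power", "accounting for an estimated 20% loss of patients". Its table gives one N per effect size and power. Test, alpha and sidedness are not stated, and no section sets out an analysis model for POSAS-O.

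Three other places bear on the point. Exclusion criterion 11 removes patients whose breast asymmetry the investigator thinks would interfere with evaluation. Section 5.4 reveals the assignment only once intraoperative symmetry has been confirmed. Section 6.4 collects patient and operative variables, including a resection weight for each breast, for use in the analyses of scar quality.

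**The concern.** Pairing removes whatever the two breasts of a patient share. It does not remove an average difference between the two sides, which could come from operator position or handedness, order of closure, or arm dominance. Randomising to mirror-image groups lets that difference be separated from the closure effect, but only if the analysis uses the group.

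A pooled paired test does not use it. A known split between the groups then becomes residual error and, when the groups are unequal, part of it enters the estimate. Because no analysis is written down, nothing ensures that the group will be used.

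**Working it through.** **1. The plan's own figure.** Exact noncentral-t power for a one-sample (paired) t-test, two-sided 5%, gives:

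| Power | d=0.2 | 0.3 | 0.4 | 0.5 |
|---|---|---|---|---|
| 80% | 199 | 90 | 52 | 34 |
| 85% | 227 | 102 | 59 | 38 |
| 90% | 265 | 119 | 68 | 44 |

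All 12 cells match section 2.2. At d=0.5 and 80% power, a one-sided test would need 27, a normal approximation 32, and a two-sample test 63 per arm. The table is therefore a plain paired test with no side term. Power is 79.5% at 33 evaluable patients and 80.8% at 34.

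**2. Inputs.** 34 evaluable patients and d=0.5 come from section 2.2. So does SD 12.5 ("the control group had a mean POSAS-O score of 20.4 (SD 12.5) at 1-year"), which the plan uses as if it were the SD of within-patient differences; 0.5 × 12.5 = 6.25 points. The side effect p (Side 2 minus Side 1 under the same closure) is not documented. I take p = 0, 0.25 and 0.5 SD, that is 0, 3.125 and 6.25 points.

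**3. Model.** Let D = FMTB minus suture, with true effect τ (the sign is immaterial here).

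- Group 1: mean of D = τ + p
- Group 2: mean of D = τ − p
- Pooled mean: τ + p(n1 − n2)/n
- Pooled SD with equal groups: about √(σ² + p²)
- Average of the two group means: τ, whatever p is, with variance σ²(1/n1 + 1/n2)/4 on n − 2 df

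At p = 6.25 the pooled SD is √(156.25 + 39.06) = 13.98 instead of 12.5.

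**4. Equal groups, 17:17.** Pooled figures are simulated; the group-term figure is exact.

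| p (SD) | Pooled power | With group term |
|---|---|---|
| 0 | 81% | 80.7% |
| 0.25 | 79% | 80.7% |
| 0.5 | 73–74% | 80.7% |

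At p=0.5 the pooled 95% interval covers about 97%, so it is conservative.

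**5. An unequal split, 21:13.** The shift is p × 8/34: 0.06 SD at p=0.25 and 0.12 SD at p=0.5. Pooled power, by direction of the imbalance, is 68% or 87% (p=0.25) and 49% or 90% (p=0.5). Type I error given this split is about 5.5% (p=0.25) or 6.8% (p=0.5). With a group term, power is 78.5% whatever p is. If allocation were simple 1:1 (an assumption), a split of 21:13 or worse among 34 would have probability 23%.

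**6. Averaged over simple 1:1 randomisation.** The pooled estimate is unbiased and type I error is about 5% at every p tried.

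| p (SD) | Pooled power | With group term |
|---|---|---|
| 0 | 80.8% | 79.5% |
| 0.1 | 80.4% | 79.5% |
| 0.25 | about 78% | 79.5% |
| 0.5 | about 72% | 79.5% |

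**The case against.** Four stronger readings are tempting, and the documents do not support them.

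*The plan's FMTB estimate is biased.* A sizing formula produces no estimate. A side term is neither specified nor ruled out, and section 6.4 foresees that patient and operative variables will enter the analyses. What can be said is conditional: if the final analysis pools the groups as the sizing does.

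*The sample size is wrong.* It is not, for this reason. With a group term and a 17:17 split, 34 patients give 80.7% power against 80.8%, so N stays at 34.

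*Type I error is inflated.* Only conditionally on an unequal split that has occurred. Over simple randomisation it is about 5%, and with equal groups the pooled test is conservative.

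*A left-right effect exists.* Nothing documents one, and the sides are not even defined. The symmetry check and exclusion 11 limit how large it could be. The striking figures need p = 0.5 SD, a side effect as large as the target treatment effect.

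Most of this stands, and it lowers the priority. It does not dispose of the point. The symmetry check precedes final skin closure, so it cannot cover differences that arise during closure or afterwards. It also relies on late unmasking, whereas section 6.3 has the whole research team told of the assignment at Visit 1; those two sections need reconciling. Exclusion 11 targets marked asymmetry in a single patient, not a small systematic difference across patients.

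**Conclusion.** The point holds as a gap in specification: the trial randomises by group, but the plan states no blocking and no POSAS-O analysis that uses the group.

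If the groups are pooled, the cost depends on an unknown side effect. At 0.25 SD or less it is at most about 2 points of power with balanced groups. With an unrestricted list, the two analyses then differ on average by only about 1 point either way. At 0.5 SD the average loss is about 7 to 8 points. The shift in the estimate matters only if a real side effect coincides with a marked imbalance.

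These figures assume 34 evaluable patients, d=0.5 and normal differences. They also accept 12.5 as the SD of within-patient differences, although the source figure is a spread of scores between patients. Minor priority.

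**What to change.** 1. Define Side 1 and Side 2 in section 5.4, and state the allocation ratio and any blocking.
2. Prespecify the FMTB effect on POSAS-O as the unweighted mean of the two group-specific mean differences. In practice, regress the within-patient difference (FMTB minus suture) on a +1/−1 group indicator and test the intercept. With complete pairs, a mixed model with fixed effects for closure and side and a random patient effect is equivalent.
3. Use permuted blocks for any envelopes not yet generated. The documents do not say how many that is.

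The cost is one degree of freedom and one model term; the group is already recorded. With 17:17, power goes from 80.8% to 80.7%. If there is no side effect and the list is unrestricted, the average loss is about 1 point (80.8% to 79.5%), and at a 21:13 split a little over 2 points (80.8% to 78.5%). Blocking removes most of that loss. The planned enrolment of 42 need not change on this account.
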